### **7.1.1 Baseline Definition**

The baseline value for analyses will be defined as the last assessment prior to the start of treatment, unless otherwise specified.

Study Day 1 will be considered as the first dose of treatment. Note that randomization may occur before study Day 1.

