#### **4.1.2     *Exclusion Criteria***

1. In the opinion of the investigator, progression to death is imminent and inevitable within the next 24 hours, irrespective of the provision of treatments
2. Currently intubated or intubated between screening and randomization
3. Suspected active uncontrolled bacterial, fungal, viral, or other infection (besides COVID-19)
4. Prior allogenic hematopoietic stem cell transplantation
5. Active lung cancer or history of lung cancer within the past 12 months
6. Any active grade 2 or higher hemorrhage
7. Any active gastrointestinal or metabolic condition that could interfere with absorption of oral medication
8. Uncontrolled intercurrent illness that, in the judgment of the treating physician, would limit compliance with study requirements
9. Known seropositivity for human immunodeficiency virus with CD4 count < 200/mm^3 within 3 months prior to randomization
10. Pregnant or breastfeeding, or positive pregnancy test in a pre-dose examination
11. Concurrent enrollment in another interventional trial (investigational COVID-19 antiviral studies are permitted)
12. Serum creatinine > 2.5 mg/dL
13. Total bilirubin > 4× the upper limit of normal
14. QT corrected by the Fridericia method (QTcF) prolongation > 480 msec
15. Known history of New York Heart Association Class II, III, or IV congestive heart failure prior to hospital admission
16. Known allergic reaction to any JAK2 inhibitor
17. Exposure to any JAK2 inhibitor within 28 days
18. Currently receiving a strong CYP3A4 inhibitor or strong P450 inducer ([Appendix 1](#) and [Appendix 2](#), respectively) and unable to stop the medication prior to the first dose of study drug and throughout the duration of study drug administration
19. Treatment with cytoreductive chemotherapy administered within 14 days prior to randomization

20. Administration of an IL-1 or IL-6 blocking immunomodulatory agent (such as tocilizumab, canakinumab, sarilumab, anakinra) within 48 hours prior to randomization
21. Currently receiving therapeutic anticoagulation or anti-platelet medication and unable to stop the medication prior to randomization. Prophylactic anticoagulation therapy or aspirin ( $\leq 100$ mg) are permitted.
22. Unable to ingest capsules or tablets at randomization

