#### **7.1.4.2        *Randomization (Study Day -1 or 1)***

Patients must have provided informed consent, then completed all Screening procedures, and met all eligibility criteria.

Note: Screening and randomization may occur on either Day -1 or Day 1. Patients may be screened, randomized, and start treatment on the same day (Day 1).

- AE reporting will begin at the time of randomization

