#### **7.1.4.3        *Study Day 1 (Pre-dose)***

Note: Patients may be screened, randomized and start treatment on the same day.

- Randomization
- 7-point ordinal scale of clinical status (unless the same time point as Screening)
- Physical examination (any physical examination performed as part of routine care on Day 1 prior to signing of informed consent may be used for documentation)
- Maximum documented temperature in the 24 hours prior to dose of pacritinib/placebo ( $T_{max}$ )
- Maximum documented heart rate in the 24 hours prior to dose of pacritinib/placebo ( $HR_{max}$ )

- Documentation of oxygen delivery method (unless the same time point as Screening). If multiple delivery methods were used, the method that provides the highest concentration of oxygen will be documented.
- Highest oxygen delivery flow rate (if on non-invasive oxygen)
- Highest %FiO2 (if on CPAP, BiPAP, or IMV)
- Highest PEEP (if on positive pressure ventilation)
- Begin pacritinib/placebo dosing
- Document pacritinib/placebo dosing
- AEs
- Concomitant medications

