## **Secondary Endpoints**

1. The number of ventilator-free days, defined as the number of days that patients are alive and not intubated, from randomization to Day 28
2. The mortality rate at Day 28 is defined as the number of patients with outcome of death during the 28 days following randomization divided by the total number of patients in the ITT population
3. The mortality rate at Day 15 is defined as the number of patients with outcome of death in the 15 days following randomization divided by the total number of patients in the ITT population.
4. The time to improvement by at least 2 points relative to Baseline on the 7-point ordinal scale of clinical status. All enrolled patients will have a score between 3 and 5 by virtue of being hospitalized and non-intubated; therefore, patients who progress from 3 to 1, from 4 to 2, or from 5 to 3 will have met the definition of improvement.
5. The clinical status as assessed by the 7-point ordinal scale of clinical status at Days 8, 15, 22, and 28.
6. The rate of use of immunomodulatory agents as treatment for COVID-19 is defined as the proportion of patients reporting use of medications such as corticosteroids, tocilizumab, anakinra, or eculizumab as treatment for COVID-19, during 28 days following randomization divided by the patients in the ITT population.

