### 6.2.3 Time to Improvement in Clinical Status

The time to improvement in clinical status from baseline will be calculated as:

- Time to Improvement in Clinical Status (days) = Date of improvement in clinical status – date of randomization + 1

The date of improvement in clinical status is defined as the first ordinal scale assessment with a decrease of 2 or more points from the baseline clinical status assessment. For example, for a patient that has a baseline clinical status of 4, the date of improvement would be the first post-baseline clinical status assessment of 2 or 1.

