##### **7.4.2.2 Mortality Rate at Day 15 and 28**

The Day 15 and Day 28 mortality rates and associated 95% confidence interval will be summarized by treatment arm.

The mortality rate at Day 15 and Day 28 will be compared between treatment arms using the CMH test stratified by age (< 60 years versus  $\geq$  60 years) and baseline 7-point clinical status scale (baseline 3 or 4 versus 5). The point estimates and 95% confidence intervals of the mortality rates at Day 15 and Day 28 will be presented by treatment arm. The CMH odds ratio, difference in mortality rates at Day 15 and Day 28, and associated 95% confidence intervals will be presented.

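### Baseline for time to improvement is taken before first dose, not at randomization, so worsening in between eases the threshold and can turn a return to the randomized score into an improvement

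*SAP*

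**What the plan says.** - **Baseline.** SAP 7.1.1: "The baseline value for analyses will be defined as the last assessment prior to the start of treatment", unless another rule is given. It defines Study Day 1 by the first dose and adds: "Note that randomization may occur before study Day 1".
- **Timing.** Protocol 7.1.4.2: "Screening and randomization may occur on either Day -1 or Day 1". Protocol 7.1.4.3 and Table 1 schedule a further ordinal score before the Day 1 dose, unless it coincides with Screening.
- **Eligibility.** Exclusion criterion 2 (Protocol 4.1.2): "Currently intubated or intubated between screening and randomization". It does not cover the time from randomization to first dose.
- **Premise on scores.** Protocol 11.1.1, secondary endpoint 4: "All enrolled patients will have a score between 3 and 5 by virtue of being hospitalized and non-intubated". The improvements it lists are 3 to 1, 4 to 2 and 5 to 3.
- **Endpoint.** SAP 6.2.3 dates improvement at the "first ordinal scale assessment with a decrease of 2 or more points from the baseline clinical status assessment" and counts days from the date of randomization. SAP 7.4.2.4 and Table 7 give no separate baseline rule for the ordinal scale.
- **Strata.** The primary CMH test in SAP 7.4.1 takes its strata from the IXRS entry. The log-rank and Cox analyses in 7.4.1, and the analyses in 7.4.2.2, 7.4.2.4 and 7.4.2.5, name the same two factors and cut-points but no source.
- **Changes.** SAP section 9 states that no departure from the protocol-specified analysis is planned.

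**The concern.** The clock starts at randomization, but the score that defines success can be taken later. Worsening after randomization should count as part of a patient's course. Here it resets the reference, and a patient who only regains the randomized score can be recorded as improved by 2 points.

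At stake is correct classification of events in a secondary endpoint that is compared between arms by log-rank test and Cox model. The protocol's definition of improvement also rests on baselines of 3 to 5, which the SAP rule does not guarantee. If strata were programmed from the SAP 7.1.1 baseline, a change in the gap could place a patient in a stratum other than the one used at randomization. A baseline of 6 would belong to no stratum.

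**Working it through.** **The plan's own figure.** The documents give no number for this endpoint. The sample size of about 200 reproduces: 13.5% versus 26.5%, one-sided alpha 0.10, 80% power and a continuity correction give 100 per arm, 2 × 100 = 200. It concerns the primary endpoint and does not change here.

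**Step 1: can the baseline follow randomization?** Yes. With randomization on Day -1 and first dose on Day 1, the Day 1 pre-dose score is the last one before treatment. On schedule the gap is about one day.

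**Step 2: can that baseline be 6?** Yes. Exclusion criterion 2 ends at randomization, and so does exclusion criterion 22 on swallowing capsules. Protocol 1.2.1 foresees giving study drug by tube to intubated patients. The ITT population keeps everyone randomized.

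**Step 3: what does the 2-point rule then do?** Let r be the score at randomization (3, 4 or 5) and b a worse pre-dose score, up to 6. Under the SAP, improvement needs a score of b − 2 or lower; with a randomization baseline it needs r − 2 or lower. A return to r counts under the SAP if b − r is at least 2.

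| r | b | Needed, SAP (b − 2) | Needed, randomization baseline (r − 2) | Drop on return to r (b − r) | Return counts? |
|---|---|---|---|---|---|
| 3 | 4 | 2 | 1 | 1 | no |
| 3 | 5 | 3 | 1 | 2 | yes |
| 3 | 6 | 4 | 1 | 3 | yes |
| 4 | 5 | 3 | 2 | 1 | no |
| 4 | 6 | 4 | 2 | 2 | yes |
| 5 | 6 | 4 | 3 | 1 | no |

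The threshold is easier in all six rows. A return to the randomized score counts in three.

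**Step 4: the opposite direction.** Improvement in the gap makes the threshold harder. A patient randomized at 5 and scored 4 before the first dose needs 4 − 2 = 2 instead of 5 − 2 = 3.

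**Step 5: link to the primary endpoint.** SAP 6.1 counts a status of 6 or 7 at any time up to Day 28, with no condition that it follow baseline. The 4-6-4 patient is therefore a primary progression and also a secondary improvement, without ever having been better than at randomization.

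**Step 6: strata.** If the SAP 7.1.1 baseline were used, 3 to 5 or 4 to 5 in the gap would move a patient from the 3-or-4 stratum to the 5 stratum, and 5 to 4 would do the reverse. A move to 6 fits neither.

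**Step 7: how many patients?** No frequency is given. Assuming that 0.5% to 5% worsen in the gap, 200 × 0.005 = 1 and 200 × 0.05 = 10 patients have a worse baseline. Only those on a path that changes the event or its date affect the result.

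**The case against.** A pre-dose baseline is a defensible choice in a double-blind trial. The change in score precedes treatment, so it should be balanced between arms on average. The gap is short, and Table 1 itself lists randomization under Day 1. Two of the three scoring paths start at 3, hospitalized without supplemental oxygen, although the definition of severe disease includes low saturation on room air. All of this stands and limits the size of the problem. It does not remove the mismatch between time origin and reference score.

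On the strata, the category 3 or 4 versus 5 is the randomization factor itself, so the ordinary reading is that the IXRS strata apply throughout. That is probably what is meant. But the source is written only for the primary CMH test, and SAP 7.1.1 gives baseline a different meaning.

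A reader might infer more than the documents support:

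- **That the sickest patients drop out of the ITT analyses.** This depends on programming. No section says so.
- **That the endpoint cannot be computed for randomized patients who are never dosed.** A Screening score is required before randomization, so a usable value exists. SAP 7.1.1 only fails to point to it.
- **That intubation in the gap escapes the primary endpoint.** SAP 6.1 already counts it.
- **That any worsening and return scores as improvement.** A one-level worsening and return does not.

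**Conclusion.** The point holds as a defect of definition in a secondary endpoint. SAP 7.1.1 allows a baseline later than randomization and outside the protocol's range of 3 to 5, and nothing in SAP 6.2.3, 7.4.2.4 or Table 7 overrides it. The result is misclassified or misdated improvement events: an easier threshold after worsening, a harder one after improvement, and false improvement on 3-5-3, 3-6-3 and 4-6-4.

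The effect is likely small. The range of 1 to 10 patients with a worse baseline rests on an assumed 0.5% to 5% and is not an estimate. A bias toward one arm might be inferred but is not expected, because these changes occur before treatment and under blinding. The primary endpoint and sample size are unaffected. The unstated source of the strata is a smaller point of clarification. The correction is still worth making, since it costs little and brings the endpoint back in line with the protocol.

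**What to change.** 1. In SAP 7.1.1, define baseline for the ordinal-scale efficacy endpoint as the last recorded score at or before randomization. This aligns the threshold with the time origin, restores the 3-to-5 premise for correctly enrolled patients and gives never-dosed patients a baseline. Keep the pre-dose baseline for safety.
2. Use the recorded score for the 2-point rule, not the IXRS entry. The documents show the IXRS only as the source of the stratum, which does not separate 3 from 4.
3. State once that all stratified CMH, log-rank and Cox analyses (SAP 7.4.1, 7.4.2.2, 7.4.2.4, 7.4.2.5) use the strata as recorded in the IXRS.
4. Leave the primary endpoint in SAP 6.1 as it is on this point.

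The cost is SAP wording and the matching programming specification. The Screening score and the IXRS stratum are already collected, and no visit or patient is added. The one downside is that efficacy and safety then use different baseline definitions, which table footnotes should make clear.

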### **7.1.2 Covariate Adjustment**

No adjustment for other covariates is planned.

### **7.1.3 Multicenter Studies**

The center effect will not be considered for this study.

### **7.1.4 Handling of Dropouts or Missing Data**

Unrecorded data values will be recorded as missing. Only recorded (i.e. complete) data values will be used for statistical analyses. In general, invalid or missing values will not be imputed in the data unless stated otherwise.

In addition, analysis methods for handling dropouts are specified under the endpoint definition.

#### **7.1.4.1 Partial or Missing AE Onset and Resolution Dates**

For AE summaries, the missing day of onset of an adverse event will conservatively be set to:

- First day of the month that the AE occurred if this is after the date of the start of first treatment.
- One day after the first treatment if this is the same month that the AE occurred.
- The 15th of the month and year if the AE month and year are before the month and year of the first treatment.

If the onset date of an adverse event is missing both day and month, it will be set to:

- January 1 of the year of onset, as long as this is after the first study treatment.
- One day after the first study treatment if this is the same year that the AE occurred.
- July 1st of the year if the AE year is before the year of the first study treatment.

If the day of resolution of an adverse event is missing, it will conservatively be set to the last day of the month or 30 days after the last dose of study treatment if this day is in the same month and year, whichever is earlier. If the day of resolution of an adverse event is missing both day and month, it will conservatively be set to the last day of the year or 30 days after the last dose of study treatment if this day is in the same year, whichever is earlier.

All missing and partial dates will be presented “as is” in listings.

### **7.1.5 Subgroup Analyses**

The following subgroup analyses of the primary endpoint may be performed:

- Age (< 60 years,  $\geq 60$  years)
- Sex (male versus female)
- Race (Caucasian versus all other races)
- Baseline 7-point ordinal scale of clinical status scale (baseline 3 or 4 versus 5)
- Baseline IL-6 (normal versus elevated)
- Procalcitonin (normal or indeterminate versus elevated)
- Ferritin (< 500  $\mu\text{g/L}$  versus  $\geq 500 \mu\text{g/L}$ )
- Other markers of disease severity (D-dimer, CRP, Troponin-I, triglycerides)

Additional subgroups may be identified on the basis of other factors including, but not limited to, use of certain medications (e.g. immunomodulatory agents) or medical history.

## **7.2 Study Population Data**

### **7.2.1 Patient Disposition**

Patient disposition will be summarized using counts and percentages for the ITT Population.

The following patient disposition categories will be summarized:

- Patients screened;
- Patients randomized;
- Patients who received study treatment;
- Patients that completed planned study treatment;
- Patients discontinued from study treatment;
- Patients that completed the study;
- Patients who discontinued the study.

For patients who discontinued study treatment and patients who discontinued the study, reason for discontinuation will be provided.

The total number of patients in each defined analysis population will be tabulated.

### **7.2.2 Demographics and COVID-19 Baseline Characteristics**

Descriptive summaries of demographic and COVID-19 disease criteria will be presented separately for the ITT Population. If other analysis populations differ from the ITT population then additional table summaries based on these populations may be presented.

Demographic characteristics may include, but are not limited to: age, sex, race, and ethnicity.

COVID-19 baseline disease characteristics may include the following: percent of patients with hypoxemia ( $\text{SpO}_2 \leq 93\%$  on room air),  $\text{SpO}_2$  for both on room air and on supplemental oxygen, type of oxygen delivery devices used (percent of patients using each device type), percent of patients with tachypnea ( $\text{RR} > 20$  breaths/min), percent of patients with  $\text{RR} > 30$  breaths/min, percent of patients with P:F  $< 300$  (among patients in whom P:F ratio was calculable), percent of patients with fever (temperature  $> 100.4\text{F}$ ), percent of patients with tachycardia ( $\text{HR} > 100$  beats/min), and baseline clinical status.

Additional summaries of disease markers of severity at baseline (normal vs above upper limit of normal) may be presented.

Demographics and COVID-19 disease criteria will be listed.

### **7.2.3 Medical History and Comorbidities**

Medical history items will be coded using MedDRA v23.1 (or later as specified in the Data Management Plan). Recorded medical history items will be summarized by System Organ Class and PT. A patient will be counted only once within each System Organ Class and PT but may contribute to more than one PT within a System Organ Class.

The number of patients with pre-defined comorbidities (e.g. diabetes mellitus) will be summarized.

Medical history and comorbidities will be listed.

### **7.2.4 Prior and Concomitant Medications**

Concomitant medications will be collected from the time of consent through 30 days following the last dose of pacritinib/placebo.

Prior medications are medications that were started and stopped prior to the first dose of study drug. Concomitant medications are medications that were taken on or after the first dose of study drug. Recorded prior and concomitant medications will be coded using the WHO Drug Dictionary (version March 2020 or later as specified in the Data Management Plan).

Recorded concomitant medications will be summarized by Anatomical Therapeutic Chemical (ATC) levels and PT. Concomitant medications of special interest (e.g. immunomodulatory agents/antiviral) will be summarized separately. A patient will be counted only once within each ATC level and PT but may contribute to more than one PT within an ATC.

Prior and concomitant medications as well as concomitant medications of special interest (immunomodulatory agents/ antiviral) will be listed.

### **7.2.5 Lung Function Assessment**

Descriptive statistics will be provided by timepoint for SpO2 in ambient air (if applicable), SpO2 with oxygen supplementation (if applicable), and oxygen delivery method.

Lung function assessments will be listed by patient.

### **7.3 Exposure to Pacritinib/Placebo**

Exposure to study treatment will be evaluated by the duration of treatment, cumulative dose, actual dose intensity, and relative dose intensity in the Safety Population.

Duration of treatment (days) is defined as the duration from first day of study treatment to the last day of study treatment, i.e.,

- Duration of treatment (days) =

Date of last dose of study treatment – date of first dose of study treatment + 1

Descriptive statistics will be provided for duration of treatment by treatment arm.

Cumulative dose (mg) is defined as the sum of all pacritinib doses of study treatment taken. Descriptive statistics will be provided for the cumulative dose. The counts and percentages of patients with any dose modifications will be provided by treatment arm. Reasons for dose modifications will also be summarized. In addition, the actual dose intensity (ADI) and relative dose intensity (RDI) will be defined as follows:

- ADI (mg/day) = (total dose taken in mg) ÷ (duration of treatment in days).
- RDI (%) = (ADI) ÷ (planned daily dose) × 100.

The planned pacritinib dose is 400 mg/day. Descriptive statistics will be provided for both ADI and RDI.

Exposure data will be listed.

### **7.4 Efficacy Analyses**

Efficacy analyses described in this section will be performed using the ITT Population according to the randomized treatment arm.

#### **7.4.1 Primary Efficacy Analysis**

The primary efficacy analysis is the proportion of patients with progression to IMV and/or ECMO or death by Day 28 in the Intent-to-Treat Population.

The primary efficacy endpoint of proportion of patients with progression to IMV and/or ECMO or death will be compared between treatment arms using the Cochran-Mantel-Haenszel (CMH) test stratified by randomization stratification factors age (< 60 years versus  $\geq$  60 years) and 7-point clinical status scale (baseline 3 or 4 versus 5) as entered in the IXRS. The point estimates and 95% confidence intervals of the proportion of patients who progress to IMV and/or ECMO or death will be presented by treatment arm. The CMH odds ratio, difference in progression rates, and associated 95% confidence intervals will be presented.

Patients who discontinued early and did not progress to IMV and/or ECMO or death (a clinical status of 6 or 7) will be considered as having progression unless they were discharged from the clinical facility (discharge date is not missing), in which case they will be considered non-progression.

To evaluate the impact of missing data on the primary analysis, two sensitivity analyses will be performed:

1. A conservative analysis in the ITT population that considers all patients who discontinued early and did not progress to IMV and/or ECMO or death (a clinical status of 6 or 7) as having progression regardless of hospital discharge status.
2. An analysis in the ITT population that considers patients who discontinue early and did not progress to IMV and/or ECMO or death (a clinical status of 6 or 7) as having non-progression.

An additional analysis of the time to event (IMV/ECMO or Death) will be performed.

The time to IMV/ECMO or Death will be calculated as the earliest date of a clinical status assessment of 6 or 7 – date of randomization + 1. Table 6 provides the rules for IMV/ECMO or death events and censoring for the time to event analysis.

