### **3.4 Sample Size Determination**

The study sample size will be approximately 200 patients (randomized in a 1:1 ratio). This provides 80% power to detect at least 13% treatment difference in the proportion of patients who progress to IMV and/or ECMO or die by Day 28, assuming that the response rate is 13.5% in the pacritinib + SOC arm and 26.5% in the placebo+SOC arm, with a one-sided Type I error rate of 0.10.

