### **6.1 Primary Efficacy Endpoint**

The primary endpoint is the proportion of patients with progression to IMV and/or ECMO or death by Day 28 (+/- 2 days) for the Intent-to-Treat (ITT) Population. Patients will be considered to have progression to IMV and/or ECMO or death based on the [Cao et al. \(Table 3\)](#) clinical status assessment of 6 or 7. Specifically, the proportion of patients with progression to IMV and/or ECMO or death by Day 28 (+/- 2 days) will be calculated in each treatment arm as:

- (Number of patients with clinical status of 6 or 7 at any time on or before Day 28 (+/- 2 days)) / (Number of patients in the ITT population)

Patients who discontinued early and did not progress to IMV and/or ECMO or death (a clinical status of 6 or 7) will be considered as having progression unless they were discharged from the clinical facility (discharge date is not missing), in which case they will be considered non-progression.

Patients will be summarized based on the randomized (planned) treatment arm. Patients can meet this endpoint in two ways by progressing to IMV and/or ECMO or dying.

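### Each missing-data sensitivity analysis gives early leavers the same outcome in both arms, so the pair does not bound the effect of dropout, and the label conservative holds only within each arm

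*SAP*

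**What the plan says.** The primary rule appears in SAP 6.1 and again in 7.4.1. It covers "Patients who discontinued early and did not progress to IMV and/or ECMO or death"; these patients "will be considered as having progression unless they were discharged from the clinical facility (discharge date is not missing"), and if discharged they count as non-progressors. The rule turns on discharge status and not on treatment arm.

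SAP 7.4.1 then adds two analyses whose stated purpose is to assess the impact of missing data:

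- Analysis 1 is described as "A conservative analysis in the ITT population that considers all patients who discontinued early" without reaching status 6 or 7. All of them count as progressors, whether discharged or not.
- Analysis 2 is "An analysis in the ITT population that considers patients who discontinue early" without such an event. All of them count as non-progressors.

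An additional time-to-event analysis (SAP 7.4.1, Table 6) censors patients lost to follow-up at their last clinical status assessment, alike in both arms. SAP 7.1.4 adds no other method for the primary endpoint and refers back to the endpoint definitions. Neither document plans an arm-specific worst case, a tipping-point analysis, a delta adjustment or multiple imputation, and neither states an expected dropout rate.

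The design level is in SAP 3.4: "The study sample size will be approximately 200 patients (randomized in a 1:1 ratio"), planned "with a one-sided Type I error rate of 0.10".

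**The concern.** A sensitivity analysis for missing data should show how far the treatment comparison could move under other assumptions about the missing outcomes. Moving both arms the same way mostly tests how the event rates move. Whether the difference moves, and in which direction, depends only on how many patients leave in each arm.

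Two consequences follow. The label conservative suggests an analysis that is hard on pacritinib, which it need not be. And the primary analysis and both sensitivity analyses can agree on a result below the design threshold when a small imbalance in the unobserved outcomes would lift it above. A reader who sees three concordant results would take the finding as robust to dropout when that had not been tested.

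**Working it through.** **The plan's own figure.** Inputs from SAP 3.4: event rates of 13.5% and 26.5%, one-sided alpha 0.10, power 80%, 1:1 allocation. The mean rate is 0.20 and the difference 0.13.

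n = [1.2816 × √(2 × 0.20 × 0.80) + 0.8416 × √(0.135 × 0.865 + 0.265 × 0.735)]² / 0.13² = (0.7250 + 0.4698)² / 0.0169 = 84.5, so 85 per arm.

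With continuity correction: (84.5/4) × [1 + √(1 + 4/(84.5 × 0.13))]² = 99.3, so 100 per arm. The stated 200 reproduces. The point below does not touch it.

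**Algebra.** Let n be the patients per arm, m_T and m_P the early leavers without an event (pacritinib, placebo), and D the placebo rate minus the pacritinib rate, with D_obs counting observed events only.

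- Analysis 2: D = D_obs
- Analysis 1: D = D_obs + (m_P − m_T)/n
- Lowest possible value (pacritinib leavers all progress, placebo leavers do not): D_obs − m_T/n
- Highest possible value (the reverse): D_obs + m_P/n

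Analysis 1 raises D when m_P > m_T, lowers it when m_T > m_P, and leaves it unchanged when they are equal. Neither analysis reaches the lower limit if any pacritinib patient leaves, except analysis 1 when no placebo patient leaves.

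**Illustration.** Assumptions: 100 per arm; 14 versus 22 observed events; leaver counts chosen for illustration. The test is an unstratified pooled z, one-sided, standing in for the stratified CMH test: z = D / √(p̄(1 − p̄) × 2/100). Event counts are pacritinib versus placebo; each cell gives D in points and p.

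| Leavers (m_T, m_P) | Analysis 1 | Analysis 2 | Lower limit | Upper limit |
|---|---|---|---|---|
| 5, 5 | 19 v 27: 8, 0.089 | 14 v 22: 8, 0.070 | 19 v 22: 3, 0.300 | 14 v 27: 13, 0.011 |
| 10, 10 | 24 v 32: 8, 0.104 | 14 v 22: 8, 0.070 | 24 v 22: −2, 0.632 | 14 v 32: 18, 0.001 |
| 3, 8 | 17 v 30: 13, 0.015 | 14 v 22: 8, 0.070 | 17 v 22: 5, 0.186 | 14 v 30: 16, 0.003 |
| 8, 3 | 22 v 25: 3, 0.308 | 14 v 22: 8, 0.070 | 22 v 22: 0, 0.500 | 14 v 25: 11, 0.025 |

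First row in full:

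- Analysis 1: p̄ = 0.23, SE = 0.0595, z = 0.08/0.0595 = 1.344
- Analysis 2: p̄ = 0.18, SE = 0.0543, z = 1.472
- Lower limit: p̄ = 0.205, SE = 0.0571, z = 0.525

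If none of the five leavers per arm had been discharged, the primary analysis equals analysis 1, so all three p-values are below 0.10.

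**Tipping point in that row.** If one pacritinib leaver progresses and no placebo leaver does, the counts are 15 v 22: p̄ = 0.185, SE = 0.0549, z = 1.275, p = 0.101.

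**Nearer the design effect.** With 14 v 26 observed and five leavers per arm, analysis 1 gives p = 0.025 and analysis 2 gives p = 0.017. The lower limit (19 v 26, 7 points) gives p = 0.118. With only three pacritinib leavers the lower limit (17 v 26, 9 points) gives p = 0.061 and stays below 0.10.

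**The case against.** Several points on the other side are fair.

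- **The label has some basis.** Analysis 1 is harsher than the primary rule because it also counts discharged leavers as progressors, and it is conservative for each arm's rate. That stands, and it is why the label needs qualifying and is not simply false. A reader might infer that analysis 1 is tilted toward pacritinib. The documents do not support that: the direction depends on which arm loses more patients, and the 8-versus-3 row shows it cutting pacritinib's advantage from 8 to 3 points.
- **Missing outcomes are actively limited.** Protocol 4.2 encourages continued follow-up after treatment stops, and Protocol 7.1.4.8 calls for record review when a discharged patient cannot be reached. SAP 7.2.1 tabulates study discontinuations with reasons. Dropout may be small, and then the question hardly arises.
- **Other output helps.** The time-to-event analysis is a further treatment of early leavers, but it censors both arms by the same rule and supplies no bound. If arm-level rates are shown for both sensitivity analyses, a reader can pair pacritinib from analysis 1 with placebo from analysis 2 and get the crude worst case. What is then missing is its stratified test and everything between the extremes.
- **The worst case is extreme.** All pacritinib leavers progressing and no placebo leaver progressing is unlikely. That stands; it should be read only as a bound. The 15 v 22 case does not depend on it.
- **Unequal dropout can show itself.** When leaver counts differ, analyses 1 and 2 give different risk differences, which alerts the reader. With equal counts there is no such signal, and the risk differences agree exactly.

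A reader might also infer that small or equal dropout removes the problem. Equal dropout removes only the gap between analyses 1 and 2; the possible range remains. Few leavers do narrow that range, by one point per leaver in an arm of 100.

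**Conclusion.** The point holds. Neither sensitivity analysis depends on arm, so together they do not bound the effect of missing data on the treatment comparison, and the one labelled conservative may move the comparison either way. In the five-per-arm illustration the three planned analyses give p between 0.070 and 0.089, while the possible risk difference spans 3 to 13 points and one additional pacritinib event is enough to cross 0.10.

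This rests on assumed dropout, an observed difference not far inside the threshold, and an unstratified test in place of CMH. The 0.10 threshold comes from the sample-size section, since SAP 7.4.1 states no level for the test. The size in the actual trial cannot be judged from the documents.

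A reader might infer that the primary analysis is biased or that the trial cannot support a conclusion. The documents do not support that: the primary test and the sample size are unaffected, and with few early leavers the matter is negligible. It is a gap in the sensitivity plan that should be closed, set against that plan's own stated purpose.

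**What to change.** In SAP 7.4.1:

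1. Drop the word conservative, or state that it refers to each arm's event rate and not to the comparison.
2. Prespecify a tipping-point table over the number of early leavers imputed as progressors, from 0 to m_T in the pacritinib arm and 0 to m_P in the placebo arm. Mark where the stratified CMH p-value crosses one-sided 0.10.
3. Include as the table's extreme corner the case with all pacritinib leavers as progressors and all placebo leavers as non-progressors. Say in the SAP that this corner is a bound and not a plausible scenario.

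Stratified results need a fixed rule for which leavers are imputed in partly filled cells, for example the range of p-values over the possible allocations to strata.

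The cost is a wording change and one extra table, with no new data and no change to the design. The drawback is that the extreme corner may look unfavourable. The change belongs in the SAP before unblinding, because SAP Section 1 labels analyses added beyond the plan as post hoc.
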